Eight months are allotted for the field trial. Participants will be enrolled on a rolling basis and participate in *SS* for 4 months in the intervention condition. After pretesting, participants will receive sun protection messages from *SS* through emails/comments based on algorithm results from their profile and activity data (see **3C.4**). All participants will complete posttest survey 4 months after randomization. They will receive links to both surveys via email and text and complete them using KB's QuestionPro software. Surveys will contain measures of self-efficacy, response-efficacy, sun protection practices, sunburn (defined as skin red and/or painful from exposure to the sun in the past four months),⁹⁶ and barriers to sun protection from the *sunZapp* and *GSS* trials (see **Boxes 1** and **2**), recall of *SS* messages (i.e., times they read the notifications; preferred type of message), and acceptability of receiving *SS* messages in future. We will assess physical activity behaviors at both pre- and posttest, using the validated International Physical Activity Questionnaire (IPAQ)^{97,98} long form and current activity data uploaded by participants to *Strava*. Intervention participants will be compensated \$65 total (\$30 pretest, \$35 posttest) and control group participants \$45 total (\$20 pretest, \$25 posttest).

3C.7. Data Management and Analysis

Focus groups will be recorded, transcribed, and analyzed using *Atlas-ti*® software by assigning codes that categorize views, themes, and opinions, rely on constant comparative analysis⁹⁹ and a phenomenological approach.^{100,101} In the pilot field trial, the primary outcome is change in sun protection pre to post, analyzed with a paired t-test; changes in perceived risk, response- and self-efficacy, and sunburn will be compared pre to post, similarly. Message recall (i.e. receipt of the messages), users' reactions, barriers, and willingness to use *SS*, will be summarized as proportions/means and compared on demographics (including if treatment differs as a function of biological sex), using chi-square tests, t-tests, and correlations at $p=0.05$ (2-tailed). We will likewise test if *SS* messages (message recall) reduced physical activity (IPAQ). Recruitment rates and duration, and follow-up rates, will be described to plan a future randomized trial on *SS*. Data will be de-identified and stored in KB's secure servers. [name] will oversee data analysis. SAS will be used for analyses.

Eligibility Criteria

Focus Group Inclusion Criteria:

- 18 years of age or older
- Able to speak and read English
- Consent to participate
- Being a regular user of *Strava* (*Strava* users group only)
- Can attend focus group in Colorado

Focus Group Exclusion Criteria:

- Having a cognitive or visual impairment that would interfere with participating
- Being unwilling to be audio/video recorded
- Having another family member participating in the research

Retrospective Activity Data Participants Inclusion Criteria:

- 18 years of age or older
- Able to speak and read English
- Consent to participate
- Being a tenured *Strava* user (member for at least one year with at least 156 activities uploaded)
- United States resident
- Able to provide authentication for data collection

Retrospective Activity Data Participants Exclusion Criteria:

- Having a cognitive or visual impairment that would interfere with participating

Usability Testing Inclusion Criteria:

- 18 years of age or older
- Able to speak and read English
- Consent to participate
- Being a tenured *Strava* user (member for at least one year with at least 156 activities uploaded)
- United States resident
- Able to provide authentication for data collection

Usability Testing Exclusion Criteria:

- Having a cognitive or visual impairment that would interfere with participating
- Having another family member participating in the research

Pilot Field Tester Inclusion Criteria

- 18 years of age or older
- Able to speak and read English
- Consent to participate
- Being a regular user of *Strava* (at least 3 uploads per week)
- United States resident

Pilot Field Tester Exclusion Criteria

- Having a cognitive or visual impairment that would interfere with participating
- Having another family member participating in the research
- Having participated in the focus group and usability testing

Age Limits

18-no maximum

Inclusion of Women and Minorities. We anticipate that 50% of the participants will be women. No exclusions for this project will be based on gender.

For the focus groups, to be held in Denver, CO, we will attempt to recruit racial/ethnic minority participants at similar rates to their representation in Denver. According to the U.S. Census, 1.4% of the population is American Indian or Alaskan Native; 3.4% Asian; 0.1% Hawaiian or Pacific Islander; 10.2% African American; 31.8% Hispanic (any race); 4.1% two or more races; and 49% White.⁸⁰

For the data acquisition, usability testing and the pilot field test, we will attempt to recruit racial/ethnic minority participants at similar rates to their representation in the United States. Potential participants will not be excluded based on race or ethnicity. According to the U.S. Census, 1.6% of the population is American

Indian or Alaskan Native; 3% Asian; 0.2% Hawaiian or Pacific Islander; 4.3% African American; 21% Hispanic (any race); 2.5% two or more races; and 67.4% White. The Targeted Enrollment Table represents a composite of these numbers.

During the recruitment process, [name] and [name] will screen for participants using protocols approved by the Western Institutional Review Board (WIRB), based on gender, race, and ethnicity. If we find that we are over-recruiting a particular gender or racial or ethnic group considering our accrual targets, we will place them on a waiting list until we have recruited an adequate number of targeted participants.

Inclusion Across the Lifespan. Children under 18 will be ineligible for participation. Children under 18 will not be enrolled in the proposed project because this program is aimed at adults and it is not possible to identify parents through the *Strava* interface to obtain parental consent. Adults of any age, who use *Strava* to track their physical activity will be enrolled (non-*Strava* adult users will also be enrolled in the focus group discussions). Age will be self-reported by the participants.

Recruitment and Retention Plan

Recruitment Procedures. Focus group participants will be recruited on a voluntary basis through Facebook and the investigators' networks in Colorado.

We will recruit 1,000 *Strava* users to provide authentication and consent to collect their retrospective (one year of data) activity data through the *Strava* API. These users will be recruited by posting invitations in clubs on *Strava*. The SS database will connect to *Strava* through its public Applications Programming Interface (API). This connection allows us to receive data of participants' physical activity from the *Strava* app when they accept our Terms and Conditions and give permission to access their data. Participants will be provided with an online consent form. They will not participate in the intervention or be contacted for follow-up surveys.

Usability testing participants will be randomly selected from those who consented to data access for creation of the outdoor activity algorithm. They will be re-contacted through the *Strava* API by email and comments (with 3 reminders over 4 weeks) and invited to participate in the usability testing. The first 30 to respond to the emails will be enrolled and receive the informed consent form before starting a condensed four-week intervention period. They will be called for a follow-up phone interview after the four-week period.

Pilot field test participants will be recruited through postings in *Strava* clubs and inviting participants to click a link to the study website to learn more about the study, where they can complete a brief screener before being provided with an informed consent form, and prompted with the authentication protocol to provide access to their *Strava* data, complete a profile with user characteristics, and complete the pretest survey.

Retention and Adherence. Participant retention and compliance with study procedures are paramount concerns. To address these factors, we have devised and implemented a retention and compliance plan. This plan addresses: 1) how participants are successfully retained throughout the course of the two-year study and 2) how participants are educated about the requirements of the program. Participants may exhibit issues that pose threats to their successful completion of the study, even though they are eligible to participate. These issues are often referred to as "red flags" in the clinical trials literature. Red flags can be circumstances, personal traits, or physical or psychological limitations that could pose potential threats to a candidates' successful retention in a long-term study. Participants may disclose these issues with the study staff publicly or privately, or study staff may suspect these issues after an interaction with a participant. Study staff will be trained on identifying red flags and other barriers to successful participation to help facilitate honest conversations with participants regarding their interest and motivation for being in the study.

To achieve the goal of high participant retention after inclusion into the program, we will use supplemental materials, personal contact, telephone reminders, motivational interviewing techniques, incentives including compensation for assessment completion, and problem solving to overcoming barriers. Participants will be compensated to incentivize and improve study retention. Participants will be compensated as follows: \$50 for participation in the focus group (higher to account for travel to KB office for focus group); \$40 for participation in the usability testing; and \$75 (\$35 at baseline and \$40 at follow-up) for participation in the pilot field test. Participants who provide access to their retrospective *Strava* activity data for development of the outdoor physical activity algorithm will be entered into a drawing for \$50 gift cards (they will not complete any surveys or participate in the intervention). The participants randomized to the no-treatment control condition in the pilot field trial will receive \$45 (\$20 at pretest; \$25 at posttest) for completing the surveys.

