1. Gather formative data from focus groups of outdoor exercisers, both *Strava* users and non-users, on interest in receiving personalized, location-based sun protection advice and willingness to use sun protection advice sent through the *Strava* mobile app before and during physical activity.
2. Develop a machine learning algorithm to predict future time of day and duration of outdoor physical activity from activities logged on *Strava* through its API from users who consent to data access.
3. Modify the algorithms in *sunZapp* and social media messages from GSS to create a prototype of the SS intervention that delivers location-based, tailored sun safety advice to *Strava* users through *Strava* comments, which can be accessed through the *Strava* website and mobile app, and emails.
4. Test with *Strava* users the acceptability of the SS prototype and sun safety messages, ways of interacting

with it, and barriers/willingness to allowing access.

The R21 research is significant and innovative. A sun protection interface for the Strava platform will allow us to identify a large population of Americans at high risk for skin cancer who routinely engage in physical activity, often outdoors with high-risk sun exposure, and reach them with sun safety advice they may not seek on their own to motivate them to practice sun safety during outdoor activities. Dissemination of evidence-based sun safety messages through this widely-used “social network for athletes” is innovative. It will help to meet the goals set by both NCI and the U.S. Surgeon General to prevent skin cancer among physically-active Americans to reverse the one cancer currently increased by physical activity.

The project will be led by Principal Investigators, [name] and [name] at Klein Buendel, Inc. (KB). *Co-Investigators at Colorado State U., [name] (project statistician) and [name] (machine learning expert) will create the predictive algorithms, assisted by a machine learning graduate student.* [name], *project consultant*, at U. of Connecticut will provide expertise on physical activity promotion and interventions delivered via social media. [name], recent software engineer at *Strava, will also serve as a project consultant* and advise on delivering the sun protection intervention through *Strava*. Media developers at KB will produce the API database and program.

3A. SIGNIFICANCE

3A.1. The Skin Cancer Problem

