In the two-year R21 research (see timeline in **Section 2.7. Form E**), we will conduct rigorous formative research and pilot-testing of the *Strava Sun* (SS) intervention. We will create study protocols in Month 1. Outdoor exercisers (Strava users and non-users) will give input on initial concepts for SS in focus groups during Months 2-5. An algorithm that predicts time of day and day of week exercising outdoors during high UV will be built using retrospective Strava user data in Months 6-8. In Months 9-15, a prototype of the SS database will be created and messages and delivery methods tested for usability/acceptability. In Months 16-21, feasibility of SS will be tested in a pilot field trial with Strava users. *While the many aims are to establish methodologic feasibility, analysis of the pilot field trial in Months 22-24 will test the hypothesis that SS will improve sun protection. To achieve the ambitious timeline, we will use protocols and methods developed in prior research (see Box 2 and 3).* All procedures will be approved by the Western Institutional Review Board.

3C.2. Target Population: Outdoor Exercisers on Strava

Target population will be users of the *Strava* social network. Inclusion criteria include a) being 18 or older, b) U.S. resident, c) engaging in regular physical activity outdoors (at least 156 times in past year [3 times per week]), and d) consenting. All participants except non-Strava users in focus groups will: e) be tenured *Strava* members (for 1+ full calendar year), f) upload at least 13 activites to *Strava* in past month (i.e., 3 per week), and g) give permission for us to access their activity data. *Strava* has 42 million members worldwide, providing a very large user population. *All recruiting, besides for focus groups, will occur by invitations through Strava (e.g., posting in clubs). Interested users will click a link to a study registration website. We cannot screen users based on inclusion criteria on Strava directly, so interested trial participants will complete a screener on the study website to determine eligibility. We expect participants to regularly participate in outdoor exercise, thus being a high-risk group, and to actively use Strava.*

3C.3. Formative Focus Groups (Specific Aim 1)

Four **focus groups** will be conducted with adults who engage in outdoor physical activity and use *Strava*, or not, in Colorado in Months 4-5 (compensation=\$50).

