The feasibility of the *SS* intervention with adults *Strava* users ($n=226$) who consent to provide activity data will be tested in a pilot field test using a randomized pretest-posttest controlled design. Participants will be recruited through posts in *Strava* clubs. They will click on a link to learn more about the study and complete a screener (eligibility: 18 or older; reside in the United States; read/write in English; upload outdoor activity to *Strava* ≥ 3 times per week) and then be provided with a) consent form, b) authentication protocol to permit access to their *Strava* data, and c) pretest survey. Once our target sample is recruited ($n=226$ *Strava* users), we will disconnect the authentication. Based on our pilot data (**Box 1**), we anticipate that 41% will be high users (upload 5+ days per week) and 43%, medium users (upload 2-4 days per week). Participants will be randomized to either *SS* or untreated control group in a 3.5:1 ratio. Power analysis was estimated using treatment effect sizes from our *sunZapp* trials (**Box 2**). For this small-scale pilot test, we powered on the quasi-experimental pretest-posttest comparison within the *SS* group, using a paired samples t-test. Assuming an effect size of 0.23 in sun protection pre to post and a correlation between the pre/post scores of 0.5, , we will need 181 participants with complete pre-post data to detect an effect of this size with power of 0.80 in a 2-tailed $p=0.05$ test, which we factored up to 226 to account for 20% attrition. A small control group ($n=50$) will be included to see if a no-treatment control condition is acceptable to users and estimate follow-up rates for planning a randomized trial. It is not designed to test for statistical differences with the treatment group.

Randomization should assure that the control group is similar on age, gender, and activity level.

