3. **Usability Test Participants (n=30):** Usability testing of the intervention will be conducted with 30 *Strava* users who previously consented to provide their data for analysis and creation of the algorithm (see above). These participants will have already provided consent for data access, but will be re-contacted by email through the *Strava* API to ask if they are interested in participating in the usability testing. The first 30 *Strava* users to respond to the emails will be enrolled and will receive informed consent before starting a condensed intervention period. Identifying the 30 participants in the SS database, we will send out the created messages by email and comments for four weeks. At the completion of the four-week period, participants will complete a phone interview with project staff to assess recall of messages, message delivery and timing (*e.g., if message received before next physical activity bout*), accuracy of outdoor activity predictions, and usability of and problems with SS comments/emails. *They will be asked about sun protection practices during physical activity*. Eligibility requirements include: tenured *Strava* user (member for at least one year with 156 activities);

18 or older; United States resident; can read/write in English; and provides authentication for data collection. Participants will be compensated \$40 for their time.

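### Aim 4 includes willingness and barriers to allowing access, but the pilot surveys only users who have already granted access and names no access measure

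*Combined protocol and SAP*

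**What the plan says.** **The aim.** Specific Aim 4 (section 2) covers the acceptability of the prototype and its messages, and ways of interacting "with it, and barriers/willingness to allowing access". The heading of section 3C.6 ties the pilot field trial to this aim.

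**Who enters the pilot.** Section 3C.6 describes the sample as adult Strava users "who consent to provide activity data will be tested in a pilot field test using a randomized pretest-posttest controlled design". After the screener, users are given a consent form, then "b) authentication protocol to permit access to their *Strava* data, and c) pretest survey". Recruitment Procedures repeats the order: after consent, users are "prompted with the authentication protocol to provide access to their *Strava* data, complete a profile with user characteristics, and complete the pretest survey". Section 3C.2 requires all participants except non-Strava focus-group members to "g) give permission for us to access their activity data".

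**What is measured.** Section 3C.6 and item 4 of Human Subjects Involvement list efficacy beliefs, sun protection practices, sunburn, barriers to sun protection, message recall, and "acceptability of receiving *SS* messages in future" or willingness to use Strava Sun (SS). Section 3C.7 and the Statistical Analysis Plan summarize reactions, barriers and willingness to use SS, and say that recruitment and follow-up rates will be described.

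**Other samples.** Of the usability testers, item 3 of Human Subjects Involvement says: "These participants will have already provided consent for data access". The 1,000 retrospective-data participants also authenticate and answer no survey questions. The focus groups, under Aim 1, discuss privacy concerns with 16 Strava users and 16 non-users.

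**The concern.** The pilot selects its respondents on the behaviour that one part of its aim sets out to study. A user who is unwilling to open their Strava data leaves at the authentication screen, before any survey question, and nothing in the plan asks why. Those who remain have all granted access, so that variable is constant and cannot be related to age, sex or upload frequency.

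This matters because SS cannot work without access. Section 3A.3 notes that an API application sees a user's data only if the user authorizes it, and section 3C.5.1 stresses data privacy. Acceptance at the authentication screen is therefore a main limit on the reach of SS, and the project's purpose is to establish feasibility before a randomized trial. Without an acceptance rate or decliners' reasons, the next trial would be planned without a key recruitment figure. Acceptability results could also be read as describing all eligible Strava users when they describe access-granters.

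**Working it through.** The plan gives no figure on this point to reproduce. The check traces the participant flow and then shows the possible scale.

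**Step 1: order of entry.**

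| Place | Order or rule |
|---|---|
| 3C.6 | screener, consent, authentication, pretest |
| Recruitment Procedures | screener, consent, authentication, profile, pretest |
| 3C.2 | access permission required of all but non-Strava focus-group members |
| Pilot inclusion lists (Eligibility Criteria; Human Subjects item 4) | authentication not listed |

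The pilot inclusion lists omit authentication, although the lists for the retrospective-data and usability samples include it. The first three rows still make it a required step before any pilot survey.

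**Step 2: measures and analyses.** The survey contents name barriers to sun protection and acceptability of, or willingness to use, SS. The analysis text names willingness to use SS. Neither names willingness to allow access or barriers to it. Recruitment rates are promised, but no acceptance rate at authentication is defined.

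**Step 3: what respondents can show.** Enrolment target: 226 (section 3C.6). Share of respondents who granted access at entry = 226/226 = 100%, for any true acceptance rate.

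**Step 4: possible number of decliners.** Let a be the share of consenting eligible users who accept authentication, and assume that everyone who accepts goes on to enrol. Users reaching the screen: N = 226/a. Decliners: D = 226/a − 226. The values of a are assumptions.

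| a (assumed) | N | D | 95% CI half-width for a |
|---|---|---|---|
| 0.90 | 226/0.90 ≈ 251 | ≈ 25 | 1.96 × √(0.90 × 0.10/251) ≈ 3.7 points |
| 0.70 | 226/0.70 ≈ 323 | ≈ 97 | 1.96 × √(0.70 × 0.30/323) ≈ 5.0 points |
| 0.50 | 226/0.50 = 452 | 226 | 1.96 × √(0.50 × 0.50/452) ≈ 4.6 points |

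The interval formula is approximate, because recruitment stops at a fixed number enrolled. Logging alone would thus estimate acceptance to within about 4 to 5 points.

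**Step 5: the nearest figure in the documents.** In the Box 1 workout-group survey (n=60), 89% were somewhat or very willing to download an app that uses their Strava data, and 35% were very willing. Taken as acceptance rates, these would give 226/0.89 − 226 ≈ 28 and 226/0.35 − 226 ≈ 420 decliners. They are stated intentions about a hypothetical app, not behaviour at an authentication screen, so they only suggest that the group of decliners is probably not empty.

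**The case against.** A reader might infer that willingness is 100% by construction, that no willingness rate can be obtained, and that barriers to access are never seen in the project. The documents do not support that reading.

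- The 100% holds only for access granted at entry. Willingness to use SS in future is asked of pilot participants and can vary, though only among people who granted access.
- The screener and consent come before authentication, so counts at each step could yield an acceptance rate with no change of design. What is missing is a definition of recruitment rates that includes this step.
- The focus groups discuss privacy and barriers to using SS with 32 people, 16 of whom need not grant access. These are hypothetical views from a small sample in Colorado, and not the reasons of people who declined.
- The questionnaires are not in the documents, and Potential Risks mentions questions on barriers and willingness to use the prototype. An access item may exist. Even so, it would reach only access-granters.
- Aim 4 says access without naming Strava data, and it promises neither a survey of refusers nor a population rate. Data access is the likely reading, not a stated one.

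Nor do the documents support any figure for how far acceptability would be overstated. They give neither a refusal rate nor any view from decliners. A later SS trial would presumably also enrol access-granters, so their acceptability ratings are relevant to it.

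What stands after all this is that actual decliners are unsurveyed in the pilot and no access measure is named.

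**Conclusion.** The point holds in limited form. Following the plan as written, the pilot surveys cannot answer the part of Aim 4 on barriers to and willingness for allowing access. Entry requires access, decliners are not asked anything, and no access item or analysis is specified. An acceptance rate is within reach through recruitment counts, but the plan does not commit to reporting it.

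The size can be given only as a range: about 25, 97 or 226 unsurveyed decliners per 226 enrolled, at assumed acceptance of 90%, 70% or 50%. The conclusion rests on reading access as access to Strava data, and on the stated order of steps being followed. The primary paired pre-post analysis and the sample size are not affected. This is a low-cost improvement that lets the pilot answer a part of its own aim.

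**What to change.** 1. Log, and report in the Statistical Analysis Plan's recruitment summary, the numbers screened, eligible, consented, and accepting or declining authentication. Give the acceptance proportion among consenting eligible users with a 95% CI.
2. Place two or three items after consent and before the authentication screen: willingness to let SS read Strava data, and the main barrier to doing so. Summarize them separately for those who accept and those who decline.
3. State that acceptability and willingness results collected after authentication apply to access-granters only.

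If the page order cannot change, the minimum is to report the step counts and narrow the wording of Aim 4 to users who have granted access.

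The cost is a reordering of web pages, a few items, an IRB wording change, one descriptive table and a slightly longer enrolment flow. No extra enrolment is needed. One limit remains: people who leave at the invitation or consent stage are still missed, so the acceptance rate describes club-recruited users who had already consented.
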